15.1.1.4 Subgroup Analysis

TEAEs by SOC/PT/Worst grade will be summarized according to group F from [Table 4: Subgroups and Strata](#). Only those with SOC = “Infections and infestations” will be presented.

15.2 Deaths, Other Serious Adverse Events, and Other Significant Adverse Events

15.2.1 Deaths

A summary of deaths will be provided including (clinicaltrials.gov requirement):

- Number and percentage of (all) deaths
- Number and percentage of the primary cause of death (categories: disease progression, adverse event, unknown, other)

The tabulation of TEAEs leading to death is described in Section 15.1.1.3. A listing of deaths, if any, will be provided.

In case there is no death in the trial, only the summary of death required by clinicaltrials.gov will be performed, neither tabulation of TEAE leading to death will be produced, nor the listing of death.

15.2.2 Serious Adverse Events

The tabulation of serious TEAEs is described in Section 15.1.1.3. A subject listing of serious TEAEs will be provided for PA.

15.2.3 TEAEs of Special Interest

The following events are defined as AEs of Special Interest (AESI):

- Liver AEs
 - Transaminase and bilirubin elevations, Hy's law cases
 - Hepatitis non-infectious
 - Hepatic failure, fibrosis and cirrhosis, and other liver damage-related conditions
 - Immune-medical hepatitis, alloimmune hepatitis, non-alcoholic fatty liver
- Severe Infections:
 - Serious AEs or Grade ≥ 3
 - Opportunistic infections Grade ≥ 3
- Amylase and Lipase elevations
 - Enzyme elevations Grade ≥ 3
 - Acute pancreatitis SMQ
- Seizures

AESI will be identified using Standardized MedDRA query (SMQ) if available or sponsor-defined list of search term (refer to Appendix 18.14).

An overview of AESI and related AESI will be presented by treatment group showing number and percentage of subjects experiencing AESI. AESI will be identified in listing of all TEAEs.

15.3 Clinical Laboratory Evaluation

The following laboratory parameters will be measured during the trial as part of the safety evaluation:

- Hematology,
- Biochemistry, including the following supplementary liver function tests (LFT):
 - Aspartate aminotransferase,
 - Alanine aminotransferase,
 - Alkaline phosphatase,
 - γ -Glutamyl-transferase,
 - Bilirubin (total),
- Urinalysis,
- Coagulation.

The clinical laboratory safety tests to be measured in this trial are provided in the protocol (refer to Section 7.4.3 Table 11 of the CTP). Parameters from the Section 7.4.3 of the CTP to be summarized and listed in the TLFs are provided in Appendix 18.12.

All laboratory data results will be presented using international system of units (SI).

Clinical laboratory findings (hematology, biochemistry, urinalysis, coagulation) will be summarized by treatment using descriptive statistics at baseline and each post baseline visit for absolute value and changes from baseline (see Section 8.2.3), excluding coagulation laboratory findings which will be summarized only at the screening visit.

Some laboratory results will be classified according to NCI-CTCAE Version 4.03 as provided by the central laboratory. In case a laboratory parameter has bi-directional toxicities (e.g., Potassium) both directions will be presented for the given parameter (i.e., Potassium Low and Potassium High).

On-treatment values are results of assessments done from the first IMP administration on Day 1 till End of Study (completion or early termination).

Laboratory results containing a modifier such as “<” or “>=” will be handled case by case for summary statistics (see Appendix 18.13) and will be reported as collected in the database and as imputed in subject data listings.

A shift table of baseline versus post-baseline based on the worst NCI-CTCAE grade will be presented by treatment group for hematology and biochemistry.

Subject data listings will be provided, with a flag for abnormal values, along with corresponding normal ranges:

- Laboratory gradable parameters part of NCI-CTCAE will be presented according to the categories based on normal ranges along with the grade. Abnormal values will be flagged according to the direction of toxicity as detailed in Appendix 18.12 (e.g., for a parameter such as Potassium Low, only values below the LLN will be flagged).
- Laboratory parameters that are not part of NCI-CTCAE will be presented according to the categories based on normal ranges: below normal limits (Low), within normal limits (Normal), and above normal limits (High). Values that are either above ULN or below LLN will be flagged.

For subjects with a gap greater than or equal to 2 weeks between 52-Week treatment period and LTE treatment period, laboratory data collected during the gap period will be presented in specific data listings.

Boxplots of the laboratory values by treatment group and time point will be provided for the following parameters of Table 30:

Table 30: Laboratory Parameters

Category	Laboratory parameter	Conventional Unit	SI Units
Hematology	Hemoglobin	g/dL	g/L
	Red blood cell count	10 ⁶ /μL	10 ¹² /L
	Reticulocyte count	10 ³ /μL	10 ⁹ /L
	White blood cell count	10 ³ /μL	10 ⁹ /L
	Neutrophil count	10 ³ /μL	10 ⁹ /L
	Lymphocyte count	10 ³ /μL	10 ⁹ /L
	Platelet count	10 ³ /μL	10 ⁹ /L
Biochemistry	Alanine aminotransferase (ALT)	U/L	U/L
	Albumin	g/dL	g/L
	Aspartate aminotransferase	U/L	U/L

	(AST)		
	Gamma-glutamyl transferase (GGT)	U/L	U/L
	Alkaline phosphatase	U/L	U/L
	Total bilirubin	mg/dL	μmol/L
	Amylase	U/L	U/L
	Lipase	U/L	U/L
	eGFR	mL/min/1.73m ²	mL/min/1.73m ²
	Blood urea nitrogen (BUN)	mg/dL	mmol/L

If consistent with BOA standards, the ULN and LLN will be added to the lab parameter boxplot, for any lab parameter where the normal range is the same for all subjects in the analysis set.

In addition, the following graphical displays will be provided:

- ALT values over time will be presented in a spaghetti plot for subjects with ALT grade 2 or higher elevation (i.e. grade ≥ 2) by treatment group
- Time in weeks from first dose to first ALT assessment of grade 2 or higher elevation (i.e. grade ≥ 2) for all subjects by treatment group (KM plot)
- Time in weeks from first dose to first eGFR assessment equal to less than 60 mL/min/1.73m² for subjects with a baseline assessment greater or equal than 60 mL/min/1.73m² by treatment group (KM plot)
- e-DISH (Evaluation of Drug-Induced Serious Hepatotoxicity) figure, as described in *Merz et al* (2014) will be presented including 5 panels: one for each evobrutinib dose group, one for all dose groups combined and one for placebo

For the 2 time-to-event figures, a subject reaching the end of study without experiencing the event will have his/her event time right-censored at the time of the last ALT/eGFR assessment or at day 398 (W56 SFU study day + 5) if last assessment is performed after. To be included in a time-to-event figure, a group must have at least one event. Below the horizontal axis of the time-to-event figure, # of subjects at risk will be displayed. The vertical axis may be restricted to 0.50 – 1.0, if none of the curves reach 50%. For LTE time-to-event figures, the starting point will be the Baseline of 52-week treatment period.

In this study, clinically significant lab abnormalities were recorded as adverse events. In lieu of a listing of clinically significant lab abnormalities for each domain, the following by-subject lab value listings will be provided:

- Listing of Grade ≥ 3 hematology values
- Listing of Grade ≥ 3 biochemistry values

- Listing of urinalysis with value ≥ 2 times ULN (excluding values for pH), or an increase of “++” for non-gradable parameters when applicable (for PA only).
- Listing of Grade ≥ 2 AST, ALT or Bilirubin. For each parameter, when a subject has an increase to Grade 2, all posterior values will be included in the listing.

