9.2 Presentation of Tables/Listings/Figures (TLFs)

Tables and figures will be sorted by treatment group (in the order stated in Table 6) and chronological time point (where applicable).

Table 6: Treatment Groups and Regimens

Treatment Group	Regimen	Presentation for the PA	Presentation for the LTE analysis (*)
1	Placebo	Placebo	Placebo/Evobrutinib 50 mg BID
2	Evobrutinib 25 mg QD (once daily)	Evobrutinib 25 mg QD	Evobrutinib 25 mg QD/Evobrutinib 50 mg BID
3	Evobrutinib 75 mg QD	Evobrutinib 75 mg QD	Evobrutinib 75 mg QD/Evobrutinib 50 mg BID
4	Evobrutinib 50 mg BID (twice daily)	Evobrutinib 50 mg BID	Evobrutinib 50 mg BID/Evobrutinib 50 mg BID

(*): Subjects who complete the 52-week Double-blind placebo-controlled period will be offered participation in an optional open label, LTE period for an additional 2 years. During this LTE period, subjects will be administered evobrutinib at an initial dose of 50 mg BID or the eventual Phase III dose, when decided.

All data recorded during the trial will be presented in individual data listings (in the order stated in Table 6). All listings are sorted by treatment group, subject, and time point (where applicable), if not otherwise stated.

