Time to first flare, flare-free status and annualized flare rate	
Time to first flare, flare-free status and annualized flare rate will be analyzed as in Section 14.3.2 at Week 24, Week 52 and Week 104 with descriptive statistics only. No statistical modeling will be performed.
 
Time to first flare will be assessed starting from randomization (Day 1 of 52-week treatment period) and will be derived for the whole treatment period.
 
Flare analyses will be censored at the time of announcements to the sites of study early termination (i.e. 23 March 2020)

15 Safety Evaluation

For all safety endpoints, data selection for PA and LTE analysis will be handled as indicated in the [Table 26](#).

Table 26 : Data Handling for Safety Analysis

Data summarized	Analysis	Analysis sets	Period covered	Treatment groups

 • AEs • Laboratory data • Vital signs • ECGs • Other safety evaluations 	PA	SAF	All data from 52-week treatment period (safety follow-up included)	
 • Placebo • Evobrutinib 25 mg QD • Evobrutinib 75 mg QD • Evobrutinib 50 mg BID
	LTE analysis	LTE SAF	All data from LTE period (safety follow-up posterior to LTE included)	
 • Placebo/Evobrutinib 50 mg BID • Evobrutinib 25 mg QD/Evobrutinib 50 mg BID • Evobrutinib 75 mg QD/Evobrutinib 50 mg BID • Evobrutinib 50 mg BID/Evobrutinib 50 mg BID

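### Section 15.3 does not limit its Day 398 censoring cap to the primary analysis, so as written the LTE Kaplan-Meier figures for ALT and eGFR are invalid after Day 398

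*SAP*

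**What the plan says.** Section 15.3 (Clinical Laboratory Evaluation) lists two time-to-event plots by treatment group. The first is "Time in weeks from first dose to first ALT assessment of grade 2 or higher elevation". The second is time to first eGFR below 60 mL/min/1.73m² in subjects at or above 60 at baseline.

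One censoring rule covers both. It opens "For the 2 time-to-event figures, a subject reaching the end of study without experiencing the event" and says that such a subject is "right-censored at the time of the last ALT/eGFR assessment", or "at day 398 (W56 SFU study day + 5) if last assessment is performed after". The cap is stated for event-free subjects only. Nothing is said about events that occur after Day 398.

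The same paragraph adds "To be included in a time-to-event figure, a group must have at least one event", and ends "For LTE time-to-event figures, the starting point will be the Baseline of 52-week treatment period". No separate censoring day is given for the LTE figures.

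Elsewhere, the footnote to Table 6 (Section 9.2) describes an "optional open label, LTE period for an additional 2 years". Table 26 (Section 15) sets the safety data for the LTE analysis as "All data from LTE period (safety follow-up posterior to LTE included").

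**The concern.** Day 398 belongs to the 52-week period, since it is that period's own follow-up visit plus five days. With the LTE clock starting at the 52-week baseline, a subject who rolls over directly starts LTE dosing near Day 365. Nearly all LTE follow-up therefore lies beyond the cap.

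Kaplan-Meier estimation requires that censoring at a given time does not depend on what happens later. Here a subject leaves the risk set at Day 398 because no event was ever seen, and stays in because one will be seen. After Day 398 the risk set consists only of future cases.

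Liver adverse events are listed as events of special interest in Section 15.2.3, and Section 7 says that the LTE analysis is reduced to focus on safety. An onset curve that drops to zero because of a censoring rule would misrepresent hepatic or renal risk in that report.

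**Working it through.** **1. The plan's own figure.** The SAP's day convention is Week 52 = 52 × 7 + 1 = Day 365 (Table 53). Week 56 = 56 × 7 + 1 = Day 393, and 393 + 5 = 398. The stated cap is reproduced.

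**2. How much LTE lies before the cap.** With direct roll-over, LTE Day 1 is about Day 365.
- LTE time before the cap: 398 − 365 = 33 days.
- Planned LTE end: 365 + 104 × 7 = Day 1093.
- Table 55 has 13 liver-test visits after LTE Day 1 (Weeks 2, 4, 6, 8, 10, 12, 14, 16, 24, 40, 52, 76, 104). Week 4 falls at 365 + 28 = Day 393 and Week 6 at 365 + 42 = Day 407. Two visits precede the cap and 11 follow it.
- Table 53 (chemistry) has 8 visits after LTE Day 1, starting at Weeks 4 and 8. Week 8 is 365 + 56 = Day 421, so one visit precedes the cap and 7 follow it.

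**3. What the rule does to the estimator.** The product-limit estimate multiplies 1 − d/n over event times, where d is the number of events and n the number at risk. Suppose m events at distinct times after Day 398 are kept and every event-free subject has left by Day 398. The numbers at risk are then m, m − 1, …, 1, and the last factor is 1 − 1/1 = 0. Tied events give the same result, because at the last event time everyone still at risk has the event. So the curve ends at exactly 0 whenever m ≥ 1, whatever the true risk. Up to Day 398 it is unchanged.

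**4. Worked example (assumed data).** 100 subjects, events on Days 100, 200, 450, 600 and 750, and 95 event-free subjects last assessed on Day 800.

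| Day | At risk, censored at last assessment | S | At risk, Day 398 cap | S |
|---|---|---|---|---|
| 100 | 100 | 0.99 | 100 | 0.99 |
| 200 | 99 | 0.98 | 99 | 0.98 |
| 450 | 98 | 0.97 | 3 | 0.98 × 2/3 = 0.653 |
| 600 | 97 | 0.96 | 2 | 0.653 × 1/2 = 0.327 |
| 750 | 96 | 0.95 | 1 | 0.00 |

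**5. How often this would happen.** The SAP gives no event rate, LTE arm size or follow-up distribution, so these are assumed: 75 subjects per arm, last assessment uniform on Days 380 to 900, constant hazard, 2,000 simulated arms per rate. Mean S is taken over arms with at least one event.

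| Hazard per year | Curve reaches 0 | Flat after Day 398 | No event, arm not drawn | Mean S(899), last assessment | Mean S(899), cap |
|---|---|---|---|---|---|
| 1% | 37% | 34% | 29% | 0.968 | 0.469 |
| 2% | 61% | 32% | 7% | 0.948 | 0.331 |
| 5% | 91% | 9% | 0.2% | 0.885 | 0.083 |
| 10% | 99% | 1% | 0% | 0.787 | 0.013 |

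**6. The other reading.** If events after Day 398 were cut as well, the curve would be valid but would stop 33 days into a planned 728-day extension (33/728 = 4.5%). That does not fit Table 26, which calls for the LTE data including the follow-up after it.

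**The case against.** The strongest reply is that the cap names the Week 56 follow-up visit and so identifies itself as a rule for the 52-week period; the LTE sentence comes later and only sets the origin. That is a plausible intention. But the rule is introduced for both figures without restriction, the LTE is added in the same paragraph, and no other LTE censoring time appears. Other parts of the SAP do set one: exposure-adjusted incidence rates (15.1.1.3) run to the end of follow-up for the period summarised, and LTE flare analyses (14.6) have a cut-off of 23 March 2020.

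The second reply is about weight, and it stands. These are descriptive plots with no test or decision attached, and the study was terminated after the primary analysis was reviewed. Late elevations can also be seen in the worst-grade shift tables, the ALT spaghetti plot, the listing of grade 2 or higher values and the LTE incidence rates. The 3-tier approach, with transaminases as Tier 1, applies to the primary analysis only, so it does not raise the stakes for the LTE.

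A reader might also infer more than the text supports:
- *Every event-free subject is censored at Day 398.* No. Those last assessed earlier are censored at that assessment.
- *The LTE curves always fall to zero.* No. An arm needs at least one retained event after Day 398; otherwise its curve stays flat, or the arm is not drawn.
- *LTE subjects carry a guaranteed event-free year.* Entry requires completing 52 weeks (Table 6 footnote), not freedom from ALT or eGFR events.
- *The 52-week origin is itself an error.* It is a deliberate choice, consistent with Section 9.6 and with LTE time to first flare in Section 14.6.
- *Leaving out zero-event arms hides the comparator.* It is a display convention. The missing curve is a flat line at 1.0, and the arm is reported in the shift tables, boxplots and, for placebo, its own e-DISH panel. The LTE has no concurrent placebo arm in any case.

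**Conclusion.** The point holds for the LTE figures. Applied as written, the censoring rule depends on the outcome after Day 398, and both Kaplan-Meier figures are invalid from there on. The drop to exactly 0 in any arm with a later event follows from the rule alone. How many arms would be affected, and by how much, rests on the assumed rates and follow-up above. If events are cut too, the figures are valid but show about 33 days of LTE. The curves up to Day 398 are correct, and the primary analysis figures are unaffected because their follow-up ends around Week 56. Severity is moderate: the stated rule gives a wrong picture, but in descriptive safety displays backed by other outputs.

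**What to change.** In Section 15.3:
- State that the Day 398 cap applies to the primary analysis figures only.
- For the LTE figures, censor event-free subjects at their last ALT/eGFR assessment, LTE safety follow-up included. Alternatively, set one LTE cut-off and apply it equally to events and non-events.
- The 52-week time origin may stay.
- Optional: drop the at-least-one-event condition and draw zero-event arms as a flat line at 1.0 with numbers at risk.

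The cost is one or two sentences of SAP text and a change to the censoring derivation in the time-to-event dataset. No new data are needed, and the primary analysis figures do not have to be rerun.

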15.4 Vital Signs

Vital signs (height (m), weight (kg), BMI (kg/m²), body temperature (°C), SBP (mmHg), DBP (mmHg), respiratory rate (breaths/min) and pulse rate (beats/min)) will be summarized by treatment group using descriptive statistics (see Section 8.2.3).

The descriptive statistics will be presented as follows:

- The baseline will be presented first
- Then each scheduled time point will be presented on subjects who have reached this time point: absolute values, CFB and percent CFB will be displayed (except for height and BMI as they are only collected at screening visit).

Body temperature, SBP, DBP, respiratory rate and pulse rate will be analyzed with shift tables of maximum CFB using the categories defined in Table 31 or PA; for FA, only SBP and DBP will be presented in shift tables:

Table 31: Vital Signs Categories

Parameter	Unit	Shift	Baseline categories	Post-baseline categories (absolute change)
Temperature	°C	Increase	<37 / \geq 37 - <38 / \geq 38 - <39 / \geq 39 - <40 / \geq 40	\leq 0* / >0 - <1 / \geq 1 - <2 / \geq 2 - <3 / \geq 3
Pulse rate	bpm	Increase and decrease	<100 / \geq 100	\leq 0* / >0 - \leq 20 / >20 - \leq 40 / >40
SBP	mmHg	Increase and decrease	<140 / \geq 140	\leq 0* / >0 - \leq 20 / >20 - \leq 40 / >40
DBP	mmHg	Increase and decrease	<90 / \geq 90	\leq 0* / >0 - \leq 20 / >20 - \leq 40 / >40
Respiratory rate	breaths/min	Increase and decrease	<20 / \geq 20	\leq 0* / >0 - \leq 5 / >5 - \leq 10 / >10

* This category will include the subjects with no changes or decrease/increase in the increase/decrease part of the table respectively.

A listing of maximum CFB and a listing of all vital signs data will be provided.

15.5 12-Lead Electrocardiogram (ECG)

The 12-lead ECG data will be listed and summarized for observed values and CFB values by treatment group using descriptive statistics for PA:

- Rhythm (sinus rhythm, atrial fibrillation, other)
- Ventricular rate (beats/min)
- PR interval (ms)
- QRS duration (ms)
- QT (ms)
- Fridericia corrected QT (QTcF) (ms).

QTcF values will be presented into the following categories:

- ≤ 430 ms,
- $> 430 - 450$ ms,
- $> 450 - 480$ ms,
- $> 480 - 500$ ms,
- > 500 ms

and categorized according to their CFB into the categories

- ≤ 30 ms,
- $> 30 - 60$ ms,
- > 60 msec.

Listings of ECG quantitative values, morphological and rhythm results will be produced.

A shift table of rhythm results, from baseline to the end of 52-week treatment period (LTE period respectively for the LTE analysis), of the number and percentage of subjects for each category (Sinus rhythm, Atrial fibrillation, Other, Missing and Total) will be provided.

A shift table of morphological assessments, from baseline to the worst observation of the 52-week treatment period (LTE period respectively for the FA), of the number and percentage of subjects for each interpretation category (Normal, Abnormal-NCS, Abnormal-CS, Missing, and Total) will also be provided.

15.6 Physical Examination

No summary table will be provided since physical examination findings during screening will be recorded as medical history events and findings during the trial as AEs.

15.7 Pregnancy Test

Results of pregnancy test (urine or serum) will be listed.

15.8 Serum IgG, IgA, IgM Levels

Boxplots of Serum IgG, IgA and IgM levels (g/L) by treatment group and time point will be provided, as well as Line plots of median percent change from baseline by time point and treatment group.

Descriptive statistics (absolute value, change from baseline and percent change from baseline) by treatment group and time point will be performed as well.

Serum IgG, IgA, IgM and IgG subclass levels will be listed by treatment group, subject and time point (where applicable). IgG values < 3 g/L (severe hypogammaglobulinemia) and IgG values < 6 g/L (hypogammaglobulinemia) will be flagged in the listing.

15.9 Total B Cell Count

A boxplot of Total B cell count (cells/ μ L) by treatment group and time point will be provided, as well as Line plots of median percent change from baseline by time point and treatment group.

Descriptive statistics (absolute value, change from baseline and percent change from baseline) by treatment group and time point will be performed as well.

Total B cell counts will be listed by treatment group, subject and time point (where applicable).

15.10 Urinalysis Microscopic Evaluation

Urinalysis Microscopic Evaluation data will be listed by treatment group and time point (where applicable).

15.11 Columbia- Suicide Severity Rating Scale (C-SSRS)

The Columbia-Suicide Severity Rating Scale (C-SSRS) is a numerical score derived from 10 categories. The C-SSRS assesses the suicidal behavior and suicidal ideation in subjects.

Occurrence of suicidal behavior is defined as having answered “yes” to a least 1 of the 4 suicidal behavior subcategories (actual attempt, interrupted attempt, aborted attempt, and preparatory acts or behavior).

Occurrence of suicidal ideation is defined as having answered “yes” to at least one of the suicidal ideation sub-categories (wish to be dead, non-specific active suicidal thoughts, active suicidal ideation with any methods [not plan] without intent to act, active suicidal ideation with some intent to act [without specific plan], and active suicidal ideation with specific plan and intent).

Occurrence of suicidality is defined as having at least one occurrence of suicidal ideation or at least one occurrence of suicidal behavior.

For the PA and LTE analysis, the number and percentage of subjects with occurrence of suicidal behavior, occurrence of suicidal ideation and occurrence of suicidality will be summarized over time. Subject data listings will be also provided.

